Primary To explore the safety and tolerability of single and multiple doses of LY3154885 in healthy subjects	Incidence of treatment-emergent adverse events (TEAEs)
Secondary 
• To determine the pharmacokinetics (PK) of LY3154885 following administration of single and multiple oral doses of LY3154885• To determine the PK of LY3154885 when administered with itraconazole (Part B only)• To assess safety and tolerability of LY3154885 when administered with itraconazole (Part B only)• To compare the PK of LY3154885 when administered with a capsule or tablet formulation (Part D only)• To evaluate the effect of a high-fat diet on the PK of LY3154885 (Part D only)	Maximum observed drug concentration (C_{max}), time to C_{max} (t_{max}), and area under the concentration versus time curve (AUC) of LY3154885 C_{max} and AUC for LY3154885 alone and in the presence of itraconazole TEAEs C_{max} , t_{max} , and AUC of LY3154885 for capsule and tablet formulations C_{max} , t_{max} , and AUC of LY3154885 with and without a high-fat diet

Summary of Study Design:

Study J1Z-MC-HUAA is a Phase 1, single-center study in healthy subjects to be conducted in 4 parts:

- Part A will be a subject- and investigator-blind, placebo-controlled, randomized, single-ascending dose, 3-period crossover study to evaluate safety, tolerability, and PK of LY3154885 in 2 alternating cohorts.
- Part B will be a subject- and investigator-blind to LY3154885/placebo, single period, drug-drug interaction study with itraconazole.
- Part C will be a subject- and investigator-blind, placebo-controlled, randomized, 14-day multiple-ascending dose, parallel-group, 3-cohort, single-period study to evaluate safety, tolerability, and PK of LY3154885.
- Optional Part D will be an open-label, 3-period, 3-sequence PK study of LY3154885 administered using a capsule or tablet formulation. Part D will also include a pilot food effect evaluation.

Treatment Arms and Planned Duration for an Individual Subject:

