	Screening	Periods 1, 2, and 3					ED	Follow-up	Comments
Procedure	-28 to -3 days prior to dosing in Period 1	Day -2	Day -1	Day 1	Day 2	Day 3		At least 7 days after final dose	
Informed consent	X								
Admission to CRU		X (Period 1)	X (Periods 2&3)						
Discharge from CRU						X			
Medical history	X								
AE/medication review			X	X	X	X	X		
Height/weight	X						X	X	Height at screening only.
Neurological exam (hours)	X			Predose, 4, 8	24	48	X	X	
LY3154885/Placebo administration (hours)				0					
Vital signs (BP, PR [supine], temperature) (hours)	X		X	Predose, 2, 4, 8, 12	24, 36	48	X	X	Time points may be added for each study period, if clinically indicated. On Day 1, temperature will be measured at predose only.
ABPM			X	X	X				The ABPM on Day -1 is a 24-hour collection in Period 1 only (baseline measurement). See Section 9.4.4.
Clinical laboratory tests	X	X		Predose		X	X	X	See Appendix 2, Clinical Laboratory Tests, for details. PI must review the result of Day-2 results prior to Day 1 dose in Period 1 only.
Pregnancy test	X	X					X	X	Serum test at screening and admission of Period 1 only; urine test at all other time points.
PE/MA	X			Predose			X	X	Full PE/MA at screening and prior to final discharge from the study. Symptom-directed PE/MA at all other time points and as deemed necessary by the investigator.

continued

Study Schedule Protocol J1Z-MC-HUAA (Part A: Single-Ascending Dose – 3 Study Periods) (concluded)

	Screening	Periods 1, 2, and 3					ED	Follow-up	Comments
Procedure	-28 to -3 days prior to Period 1	Day -2	Day -1	Day 1	Day 2	Day 3		At least 7 days after final dose	
Single safety 12-lead ECG (hours)	X			Predose, 2, 4	24	48	X	X	
PK sampling (hours)				Predose, 0.5, 1, 2, 3, 4, 5, 6, 8, 12	24, 36	48			Sampling times are relative to the time of study treatment administration (0 hour).
Stored non-PGx plasma sample (hours)				Predose, 8	24				Stored sample for biomarker research. Sampling times are relative to the time of study treatment administration (0 hour).
PGx sample			X						Single sample for pharmacogenetic analysis taken prior to/on Day 1 of Period 1.
Urine collection (hours)				0-12, 12-24	24-36				Urine collection time starts from actual dosing time on Day 1 and finishes within \pm 30 minutes of the 36-hour time point.
Serum creatinine				Predose					To be collected at predose and sent to central laboratory.

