5.1.1. Part A (Single-Ascending Dose)

Part A will be conducted in 2 alternating cohorts (Cohorts 1 and 2), each consisting of approximately 12 subjects who will participate in up to 3 study periods. The planned doses of LY3154885 to be tested are 15, 45, 100, 200, 400, and 500 mg (see Section [5.5](#) for details).

Sentinel dosing will be used in Part A of the study. For all dose levels, LY3154885 and placebo will be administered first to 2 subjects (1:1 LY3154885:Placebo) in a blinded manner. These subjects will be followed up for 24 hours postdose; if the dose is well tolerated, dosing of the remaining 10 subjects in the cohort at the same dose level may begin.

Each subject in Cohorts 1 and 2 will be randomized to receive 2 single oral doses of LY3154885 and 1 oral dose of placebo as a capsule formulation over 3 study periods in a crossover fashion. For each study period, it is intended that 8 subjects will receive LY3154885 and 4 subjects will receive placebo.

In Period 1, subjects will be admitted to the clinical research unit (CRU) on the afternoon of Day -2 for set up of baseline ambulatory blood pressure monitoring (ABPM) (see Section [9.4.4](#)) and on Day -1 for Periods 2 and 3. Subjects will undergo an overnight fast (Section [6.3.1](#)) before dosing with LY3154885 or placebo as a single oral dose on Day 1 and will remain inpatient for at least 48 hours after dosing (until Day 3), after which they may be discharged at the discretion of the investigator. The washout time between doses for a given subject will be at least 7 days. A poststudy follow-up visit will be conducted at least 7 days after the final dose.

All available safety data, including AEs, vital signs (blood pressure [BP] and pulse rate [PR]), ECGs, and clinical laboratory tests, from all subjects dosed will be assessed prior to escalating to

the next dose level (see Section 10.3.5). Safety data must include data from at least 2 days from a minimum of 6 subjects who received LY3154885. The investigator and sponsor will review the data, with the investigator remaining blinded. If dose escalation is terminated prior to reaching Dose 6 because of tolerability issues, previous dose levels may be repeated or lower/intermediate dose levels may be tested.

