5.1.3. Part C (Multiple-Ascending Dose)

The decision to conduct Part C will be made after review of safety, tolerability, and PK data from Parts A (SAD) and B (CYP3A4 Inhibition).

[figure not shown]
Part C will explore up to 3 dose levels in 3 separate cohorts (Cohorts 4 to 6) of healthy subjects. Each cohort will consist of approximately 12 subjects (9 LY3154885; 3 placebo) dosed daily for 14 days with a capsule formulation.

Subjects will participate in a single study period consisting of 14 days of once-daily dosing with LY3154885 or placebo; study drug will be administered as a single oral dose in the morning under fasted conditions (see Section 6.3.1). Subjects will be admitted to the CRU on the afternoon of Day -2 for set up of baseline ABPM (see Section 9.4.4) and will be required to remain in-house for at least 48 hours after dosing (Day 3), and at the discretion of the investigator. As detailed in the Schedule of Activities (Section 2), subjects will attend the CRU on Days 4, 5, 6, 9, and 10 on an outpatient basis for daily dosing and will be permitted to leave the CRU at the discretion of the investigator. Pharmacokinetic sampling will be conducted as detailed in Section 2. To assess CV effects and potential accommodation over time, ABPM will

be included on Day -1 (baseline) and on Days 1, 2, 7, 11 and 12, and 14. A poststudy follow-up visit will be conducted approximately 7 days after discharge.

The doses evaluated will be selected based on emerging data from Parts A and B and from the lower doses from Part C (see Section 5.5 for details). If the safety data do not support increasing the dose in subsequent cohorts, then a dose may be repeated or lower/intermediate doses may be explored. The PK data obtained during the study may be used to assist in dose-escalation decisions, but such data are not required for dose-escalation purposes. For the safety review prior to dose decisions between cohorts, all available safety data (AEs, vital signs, ECGs, and laboratory results) to Day 14 from at least 6 subjects taking LY3154885 must be reviewed by the sponsor and investigator. In addition, each cohort (including at least 6 subjects treated with LY3154885) will complete dosing to Day 14 prior to the next cohort being admitted to the CRU for dosing.

Figure HUAA.5.3 illustrates the study design for Part C.

Abbreviations: LY = LY3154885; PL = placebo; QD = once daily.

Figure HUAA.5.3. Illustration of study design for Part C.

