9.2.1. Serious Adverse Events

An SAE is any AE from this study that results in one of the following:

- death
- initial or prolonged inpatient hospitalization
- a life-threatening experience (that is, immediate risk of dying)
- persistent or significant disability/incapacity
- congenital anomaly/birth defect
- important medical events that may not be immediately life-threatening or result in death or hospitalization but may jeopardize the patient or may require intervention to prevent one of the other outcomes listed in the definition above

Study site personnel must alert the Lilly CP/clinical research physician (CRP), or designee, of any SAE as soon as practically possible.

Additionally, study site personnel must alert Lilly Global Patient Safety, or its designee, of any SAE within 24 hours of investigator awareness of the event via a sponsor-approved method. If alerts are issued via telephone, they are to be immediately followed with official notification on study-specific SAE forms. This 24-hour notification requirement refers to the initial SAE information and all follow-up SAE information.

Investigators are not obligated to actively seek AEs or SAEs in subjects once they have discontinued from and/or completed the study (the subject summary CRF has been completed). However, if the investigator learns of any SAE, including a death, at any time after a subject has been discharged from the study, and he/she considers the event reasonably possibly related to the study treatment or study participation, the investigator must promptly notify Lilly.

Pregnancy (maternal or paternal exposure to IMP) does not meet the definition of an AE. However, to fulfill regulatory requirements any pregnancy should be reported following the SAE process to collect data on the outcome for both mother and fetus.

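### Part A, and apparently Part C, schedules no AE review at Follow-up, so planned questioning for the primary TEAE endpoint ends soonest after the two highest Part A doses

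*Protocol*

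**What the plan says.** The only primary endpoint is "Incidence of treatment-emergent adverse events (TEAEs" (Protocol Sections 1 and 4). The Schedule of Activities (Protocol Section 2) handles AE questioning at the last visit differently by part:

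- **Part A.** The row "AE/medication review" is marked on Days -1, 1, 2 and 3 of each period and at ED. The Follow-up column, headed "At least 7 days after final dose", is empty in this row. Weight, neurological exam, vital signs, laboratory tests, pregnancy test, PE/MA and ECG are all marked there.
- **Part C.** The row carries nine marks, which fit Day -1 to Day 15 plus ED, and nothing at Follow-up. Vital signs, laboratory tests, PE/MA, ECG, PWC-20 and C-SSRS are marked at that visit.
- **Part B.** The row is marked through Day 18, at ED and at Follow-up.
- **Part D.** The row also reads as blank at Follow-up, but the columns of that table do not line up reliably in the text copy.

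The visits themselves are planned. For Part A: "A poststudy follow-up visit will be conducted at least 7 days after the final dose" (Section 5.1.1). For Part C: "A poststudy follow-up visit will be conducted approximately 7 days after discharge" (Section 5.1.3).

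Protocol Section 9.2 has site staff record AEs from consent onward and does not stop this at discharge from the unit. Section 9.2.1 adds: "Investigators are not obligated to actively seek AEs or SAEs in subjects once they have discontinued from and/or completed the study". SAP Section 9.5.1 treats any postdose onset or worsening as treatment-emergent and gives no end date. SAP Section 6 lists Part A placebo as one treatment.

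**The concern.** Section 9 sends the site to the Schedule of Activities for what is done and when. An AE row left blank at the last planned contact means that the question about new events is not scheduled there, although Sections 9.2 and 9.2.1 imply that AEs are still being sought at that point. No section explains why Part B should differ from Parts A and C.

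In Part A the effect is not the same for every dose. Periods 1 and 2 are covered by the Day -1 review of the next period. Period 3 has no next period, and under the planned order it holds the two highest doses. Part A TEAE incidence is summarised by treatment, so a difference in how long subjects are asked can look like a difference between doses. Part A tolerability also feeds the dose ceiling for Part C (Protocol Section 5.5). In Part C the unscheduled stretch is the week after 14 days of dosing stop, and withdrawal symptoms are one of the exploratory objectives.

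**Working it through.** The plan states no figure for the length of AE review, so there is none to reproduce. The check counts days from the schedule.

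**Inputs**

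- Planned doses: "The planned doses of LY3154885 to be tested are 15, 45, 100, 200, 400, and 500 mg" (Protocol Section 5.1.1). Doses 5 and 6 are therefore 400 and 500 mg.
- Dose order (Figure HUAA.5.1): Cohort 1 receives Doses 1, 3 and 5, and Cohort 2 receives Doses 2, 4 and 6, in Periods 1, 2 and 3. Period 3 holds Doses 5 and 6.
- Spacing: "The washout time between doses for a given subject will be at least 7 days" (Section 5.1.1).
- Allocation in each period of each cohort: 8 LY3154885, 4 placebo (Section 5.1.1).
- Projected half-life: about 12 hours (Section 3.2).

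**Part A: time from dose to last scheduled AE review**

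- Doses 1 to 4: Day 1 of the next period is at least 7 days after the dose, so its Day -1 review is at least 7 − 1 = 6 days after. The next Day 1 review is at least 7 days after.
- Doses 5 and 6: the last review is Day 3, which is 3 − 1 = 2 days, or 48 hours.
- Ratio: at least 6 / 2 = 3.
- Stretch between Day 3 and Follow-up with no scheduled AE review after Doses 5 and 6: at least 7 − 2 = 5 days.

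**Part A: administrations affected**

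- LY3154885: 8 × 2 cohorts × 3 periods = 48 in all; 8 × 2 = 16 in Period 3.
- Placebo: 4 × 2 × 3 = 24 in all; 4 × 2 = 8 in Period 3.
- Mean minimum window for pooled placebo: (16 × 6 + 8 × 2) / 24 = 112 / 24 = 4.7 days, against 2 days for 400 and 500 mg.

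Placebo given in Period 3 has the same 48-hour window as Doses 5 and 6. The imbalance arises against pooled placebo and against lower doses, not against concurrent placebo.

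**Part C**

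- Last dose Day 14; last scheduled review Day 15, about 24 hours later.
- Follow-up is about 7 days after the Day 15 discharge, so about Day 22. Of the 22 − 14 = 8 days after the last dose, about 7 come after the last scheduled review.

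**Drug remaining at the last scheduled review**, from 0.5^(t / 12 h)

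- Part A, Doses 5 and 6, at 48 h: 0.5^4 = 6.25%.
- Part C, at 24 h: 0.5^2 = 25%.

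**How often a late event might arise (assumption).** The documents give no late-onset rate. If each subject had a 5%, 10% or 20% chance of an AE starting after the last scheduled review, the chance of at least one such event is 1 − (1 − p)^n. That is 34%, 57% or 83% among 8 subjects at one Part A dose, and 37%, 61% or 87% among 9 at one Part C dose. These are chances that an event occurs, not that it is missed.

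**The case against.** The strongest reply is that a blank cell does not close AE collection. Section 9.2 sets no stop at discharge. Section 9.2.1 lifts the duty to seek AEs actively only after a subject has discontinued or completed the study, and Follow-up falls before completion. The SAP sets no TEAE end date. This stands. A reader might infer from the schedule that the primary endpoint loses its post-discharge window altogether; the documents do not support that.

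Nor are late events recorded only if volunteered. Part A Follow-up includes a neurological exam and PE/MA. Part C Follow-up includes PE/MA, the C-SSRS and the PWC-20, and Section 9.4.7.2 describes the PWC-20 as asking about withdrawal symptoms since the last visit. These contacts will bring out some events. They do not replace a general AE and medication question, and Part A has no symptom checklist.

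A reader might also try to size the bias. Taking a true 50% incidence with 10% to 30% of affected subjects having their first event after 48 hours gives a recorded 50% × (0.9 to 0.7) = 45% to 35%. Every input there is assumed, and it supposes that all late events are lost. If half were captured, the range would be 47.5% to 42.5%. With 8 subjects per dose, one subject is 12.5 points, so even the larger loss is 0.4 to 1.2 subjects. With about 6% of drug left at 48 hours, nothing in the documents points to substantial late onset.

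Three further limits stand. Escalation within Part A is not affected, because Section 5.1.1 requires at least 2 days of data and the Day 1 to 3 reviews supply them. The safety summaries are descriptive and the study is unpowered. The evidence for Part C is weaker than for Part A: its dosing row is also blank on Day 14, although the text doses through Day 14, so a blank in that table is not proof that an activity is omitted.

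**Conclusion.** The point holds as an inconsistency between the schedule and the text that touches the sole primary endpoint. The Part A schedule, and apparently Part C, omits AE/medication review at Follow-up, unlike Part B and in tension with Sections 9.2 and 9.2.1. Collection stays open by definition; uniform scheduled questioning does not.

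In Part A the scheduled window is 48 hours after 400 and 500 mg against at least 6 days after 15 to 200 mg. This covers 16 of 48 planned LY3154885 administrations, with 8 of 24 placebo administrations sharing the short window. It assumes that the planned escalation is completed in order; doses may be repeated, lowered or changed (Sections 5.1.1 and 7.4). In Part C the last scheduled review is about 24 hours after the last dose.

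Late-onset TEAEs at the top Part A doses could be under-ascertained relative to lower doses and pooled placebo. The direction follows if sites work from the schedule and some late events go unasked and unreported. The size cannot be derived from the documents.

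**What to change.** Mark AE/medication review at Follow-up in the Part A and Part C schedules, as in Part B, and check the Part D row against the source. Scheduled review after Doses 5 and 6 then runs to at least 7 days, in line with Doses 1 to 4, and in Part C it runs to about Day 22. It would help to state in SAP Section 9.5.1 one TEAE cut-off that applies equally to every Part A dose and to placebo.

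The cost is two or three schedule cells and a sentence in the SAP. The visit already takes place with PE/MA, vital signs, laboratory tests and ECG, so no visit or procedure is added beyond asking the question. If the schedule can no longer be changed, a supplementary table of Part A TEAEs with onset within 48 hours of dosing would put all doses and placebo on the same scheduled window.

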3.1. Study Rationale

LY3154885 has not been administered to humans. This first-in-human study will investigate the safety, tolerability, and pharmacokinetics (PK) of single and multiple doses of LY3154885 in healthy subjects. The study will also investigate the impact of cytochrome P450 (CYP) 3A4 inhibition on the safety, tolerability, and PK of LY3154885 after a single dose via a tablet or capsule formulation. The data generated in this study will be used to help design subsequent clinical studies.

3.2. Background

LY3154885 is a D1 PAM. By increasing the affinity of the D1 receptor for dopamine, a D1 PAM should amplify the response to endogenous dopamine, increasing D1 tone when and where dopamine is released. By increasing the affinity of the D1 receptor for dopamine, D1 PAMs amplify the response to endogenous dopamine, increasing D1 tone when and where dopamine is released (Svensson et al. 2017; Bruns et al. 2018).

This mode of activity is in contrast to direct acting D1 agonists, which activate all D1 receptors to which they have access for as long as they are present. Some D1 agonists also show rapid development of tolerance due to constant activation of the D1 receptor. In contrast, because the mechanism of action of a D1 PAM is dependent on endogenous dopamine tone and thus subject to normal feedback control, a D1 PAM should have a much lower propensity for overstimulation and desensitization.

LY3154885 has demonstrated a favorable safety profile in good laboratory practice (GLP)-compliant toxicology and safety pharmacology studies to support clinical trials, with cardiovascular (CV) and central nervous system (CNS) effects that are transient, monitorable,

and void of correlating adverse pathologic changes. CCI

CCI

LY3154885 has demonstrated suitable absorption, distribution, metabolism, and excretion properties in in vitro experiments and in nonclinical in vivo studies to warrant clinical investigation. The compound is lipophilic and neutral, with acceptable solubility and high permeability. It is eliminated mainly via hepatic metabolism by CYP3A4 and UDP-glucuronosyltransferase (UGT). In humans, LY3154885 is projected to have low oral clearance and a half-life of approximately 12 hours. The drug-drug interaction risk with LY3154885 is considered low based on in vitro data and projected human dose and exposures. However, since there is some uncertainty about the extent that CYP3A4 metabolism contributes to the overall clearance of LY3154885, this will be evaluated as part of this study by coadministering LY3154885 with itraconazole, a strong CYP3A4 inhibitor. Itraconazole is predicted to result in a LY3154885 area under the concentration versus time curve (AUC) that is 2.6-times the AUC when LY3154885 is administered alone.

3.3. Benefit/Risk Assessment

The nonclinical safety information for LY3154885 adequately supports the transition from preclinical status to clinical development. On the basis of the nonclinical data, LY3154885 is not considered to be a high-risk compound. This protocol reflects the fact that LY3154885 has not been administered to humans previously, and to mitigate this risk, the study will be conducted in accordance with principles outlined in the Guideline on Strategies to Identify and Mitigate Risks for First-in-Human Clinical Trials with Investigational Medicinal Products. Any potential risk could be identified early through close monitoring and surveillance, such as electrocardiograms (ECGs) and assessment of vital signs.

There is no anticipated therapeutic benefit for the subjects.

More information about the known and expected benefits, risks, serious adverse events (SAEs), and reasonably anticipated adverse events (AEs) of LY3154885 are to be found in the Investigator's Brochure (IB).

4. Objectives and Endpoints

Table HUAA.4.1 shows the objectives and endpoints of the study.

Table HUAA.4.1. Objectives and Endpoints

Objectives	Endpoints

Primary
 
To explore the safety and tolerability of single and multiple doses of LY3154885 in healthy subjects
	Incidence of treatment-emergent adverse events (TEAEs)

Secondary
 
 • To determine the pharmacokinetics (PK) of LY3154885 following administration of single and multiple oral doses of LY3154885 • To determine the PK of LY3154885 when administered with itraconazole (Part B only) • To assess safety and tolerability of LY3154885 when administered with itraconazole (Part B only) • To compare the PK of LY3154885 when administered with a capsule or tablet formulation (Part D only) • To evaluate the effect of a high-fat diet on the PK of LY3154885 (Part D only) 	
Maximum observed drug concentration (C_{max}), time to C_{max} (t_{max}) and, area under the concentration versus time curve (AUC) of LY3154885
 
C_{max} and AUC for LY3154885 alone and in the presence of itraconazole
 
TEAEs
 
C_{max}, t_{max}, and AUC of LY3154885 for capsule and tablet formulations
 
C_{max}, t_{max}, and AUC of LY3154885 with and without a high-fat diet


Exploratory (Part C Only)
 
 • To explore any procognitive effects of LY3154885 in healthy subjects using the Hopkins Verbal Learning Test (HVLT) and Digital Symbol Substitution Test (DSST) • To explore the effect of LY3154885 on subjective mood using the Profile of Mood States Second Edition (POMS-2) • To evaluate any potential withdrawal symptoms following multiple once-daily dosing of LY3154885 	
HVLT and DSST
 
Effect on mood profile
 
Responses to Penn Physician Withdrawal Checklist (PWC-20)

5. Study Design

